10.3.2 Safety Analyses

All safety analyses will be performed on the As-treated analysis population.

Endpoint	Statistical Analysis Methods
Primary	Not applicable as all safety assessments and variables are considered secondary.
Secondary	Safety assessments and variables during the 16-week placebo-controlled treatment period (TP), as specified in Table 4-1 , will be summarized descriptively by treatment group (combined BMS doses, each BMS dose, and placebo). Adverse events will be listed and tabulated by System Organ Class (SOC) and Preferred Term (PT). Categorical data will be summarized as frequency counts and percentages. Continuous data for absolute and change from baseline values will be summarized using n, mean, standard deviation, median, minimum, and maximum, unless otherwise specified.

Abbreviations: n = number of samples; PT = Preferred Term; SOC = System Organ Class; TP = treatment period.

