5.1.3 Active Treatment Period (Week 16 to Week 52)

Participants who complete the placebo-controlled treatment period will continue into an active treatment period for an additional 36 weeks of treatment.

At Week 16, participants receiving placebo during the placebo-controlled treatment period will be re-randomized 1:1 in a blinded-fashion to receive active treatment with either deucravacitinib 3 mg BID or 6 mg BID until Week 52. Participants receiving deucravacitinib 3 mg BID or 6 mg BID through Week 16 will continue on the originally randomized treatment in a blinded manner through Week 52 (Table 2-3).

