5.4 Scientific Rationale for Study Design

The primary purpose of the study is to estimate the treatment effect of deucravacitinib in participants with DLE/SCLE. CLASI will be the key efficacy assessment to provide clinical evidence of response to deucravacitinib in the CLE population. The primary endpoint will be the percent change from baseline in CLASI-A score at Week 16.

CLASI is a validated instrument that is used in lupus clinical trials to quantify disease activity and damage in CLE. CLASI was assessed for content validity, inter-rater validity and intra-rater validity, and performed well in all of these aspects.²⁹ CLASI can be used to categorize patients into severity groups and to identify clinically significant improvements in disease activity.

CLASI consists of two separate scores to allow for descriptions of both disease activity (CLASI-A) and damage (CLASI-D). This differentiation permits easily quantifiable assessments of activity in short-term studies, as well as assessments of disease-induced damage in longer-term studies. CLASI-A has been used in large Phase 2 and 3 SLE trials to document efficacy in cutaneous disease manifestations in participants with lupus.^{19,30,31} Randomized, double-blind, placebo-controlled studies in DLE/SCLE and SLE have included percent change from baseline in CLASI-A as a primary efficacy measures.³⁹

A placebo control is included up to Week 16 to allow the effects of treatment, both desired and adverse, to be appropriately attributed to treatments received, taking into account that all participants must be on a stable dose of background therapy for DLE/SCLE consisting of antimalarial and/or an immunosuppressant and /or oral corticosteroids [REDACTED].

The 16 weeks placebo-controlled treatment duration of this study is considered optimal to assess potential clinical benefits of deucravacitinib in DLE/SCLE while minimizing the duration of treatment with placebo. This duration is consistent with other studies that evaluated the effect of investigational treatment in CLE such as the Phase 2 LILAC Study of BIIB059 in Participants with Active Cutaneous Lupus Erythematosus.³⁹

The overall treatment duration of 52 weeks is considered necessary to assess the durability of therapy benefits, taking into account the chronic nature of CLE and its waxing and waning course, and to obtain 1-year safety data with deucravacitinib.

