10.2 Populations for Analyses

For purposes of analysis, the following populations are defined:

Population	Description
Enrolled	All participants who sign informed consent.
Randomized	All participants who are randomized to a treatment. Participants will be grouped according to the treatment to which they are randomized according to IRT at the start of the treatment period.
As Treated	
All participants who took at least 1 dose of double blind study treatment in the placebo-controlled part of the study.
 
The treatment group “as treated” will be the same as the treatment group “as randomized” by IRT, except in the following cases:
 
• If a participant took the same incorrect treatment throughout the study, then the participant will be analyzed based on the treatment received.• If a participant took study drug from more than one treatment group, and none of the administrations were consistent with the assigned randomized treatment group, then the participant will be analyzed based on the first treatment taken.
As-Treated (Active Treatment Period)	
All randomized participants who took at least 1 dose of double-blind study treatment in the active treatment period. Participants will be included in the treatment path they were randomized, except in the following cases:
 
• If a participant took the same incorrect treatment throughout a respective treatment period, then the participant will be analyzed based on the treatment received in each treatment period.• If a participant took study drug from more than one treatment group within a treatment period, and none of the administrations were consistent with the assigned randomized treatment group, then the participant will be analyzed based on the first treatment taken within each treatment period. 
Participants will be grouped according to the following treatment sequences:
 
• Deucravacitinib 3 mg BID □ deucravacitinib 3 mg BID• Deucravacitinib 6 mg BID □ deucravacitinib 6 mg BID• Placebo □ deucravacitinib 3 mg BID
- OR -• Placebo □ deucravacitinib 6 mg BID.

Abbreviations: BID = twice a day; IRT = Interactive Response Technology.

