10.3 Statistical Analyses

The statistical analysis plan (SAP) will be developed and finalized before database lock and will describe the selection of participants to be included in the analyses, and procedures for accounting for missing, unused, and spurious data. Below is a summary of planned statistical analyses of the primary and secondary endpoints. See [Table 4-1](#) for the list of endpoints.

A description of the participant population will be included in a statistical output report, including subgroups of age, gender and race.

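### Does section 10.3.2 place Week 16-52 safety data under the wrong treatment groups?

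*Combined protocol and SAP*

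**What the plan says.** Section 10.3.2 opens with "All safety analyses will be performed on the As-treated analysis population". It then describes one set of summaries, limited to the 16-week placebo-controlled period and presented "by treatment group (combined BMS doses, each BMS dose, and placebo").

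Section 10.2 defines two as-treated populations:

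- **As Treated:** "All participants who took at least 1 dose of double blind study treatment in the placebo-controlled part of the study". The group is the one randomized, with two exceptions for wrong treatment. The first reads "If a participant took the same incorrect treatment throughout the study, then the participant will be analyzed based on the treatment received". The second covers someone who took drug from several groups, none of it matching the assignment; that person is analyzed under the first treatment taken.
- **As-Treated (Active Treatment Period):** participants with at least one dose in that period. "Participants will be grouped according to the following treatment sequences": 3 mg throughout, 6 mg throughout, placebo then 3 mg, placebo then 6 mg. Its wrong-treatment exceptions work within each treatment period.

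Under section 5.1.3 the placebo group is "re-randomized 1:1 in a blinded-fashion to receive active treatment" at Week 16, for 36 further weeks. Section 5.4 gives as one reason for the 52-week duration "to obtain 1-year safety data with deucravacitinib". Section 10.3 introduces its content with "Below is a summary of planned statistical analyses of the primary and secondary endpoints" and says that the SAP will set out which participants enter which analyses.

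**The concern.** The opening sentence of 10.3.2 covers every safety analysis and appears to name one population, whose groups are fixed at the initial randomization. After Week 16 nobody takes placebo, so a safety table for Weeks 16-52 built on that population would file deucravacitinib events and exposure from the former placebo arm under placebo. The population that would prevent this is defined in 10.2, but no readable sentence assigns it to an analysis.

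At stake would be the longer-term safety profile. Crossover events would be missing from the dose columns, and a placebo column would contain events that occurred on active drug.

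The first As Treated exception adds a smaller worry. It asks whether the wrong treatment was taken over the whole study, although the table it serves covers 16 weeks.

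**Working it through.** **Inputs.** About 75 participants randomized 1:1:1 (section 5.2), taken as 25 per arm; an active period of 52 - 16 = 36 weeks (section 5.1.3); placebo re-randomized 1:1 (section 5.1.3). The readable text gives no retention figure, so full retention is assumed first and then varied. The documents state no figure for these exposure shares, so there is none to reproduce.

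**Planned deucravacitinib exposure, Weeks 16-52**

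- Total: 75 × 36 = 2,700 participant-weeks.
- By initial arm: 25 × 36 = 900 each for placebo, 3 mg and 6 mg.
- By sequence: 900 (3 mg throughout), 900 (6 mg throughout), and 12.5 × 36 = 450 for each placebo sequence.
- Share that the two groupings treat differently: 900 / 2,700 = 33.3%.
- Taken at each dose: 900 + 450 = 1,350. Initial-arm grouping would put 900 / 1,350 = 66.7% of this under the dose label.

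**Unequal retention.** With retention p in the placebo arm and a in each active arm, the share is p / (p + 2a). Over an assumed range of 70% to 100% it runs from 0.7 / 2.7 = 25.9% to 1 / 2.4 = 41.7%.

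These figures show what a Week 16-52 table by initial arm would do. The next question is whether the plan contains one.

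| Text | Period covered | Grouping |
|---|---|---|
| 10.3.2, described summaries | 16-week placebo-controlled | pooled doses, each dose, placebo |
| 10.2, As Treated | placebo-controlled part | initial arm |
| 10.2, As-Treated (Active Treatment Period) | active treatment period | four sequences |

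The first two rows match. The third has no described table, and no described table uses initial-arm grouping after Week 16.

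**Wrong-treatment rule.** Take a participant randomized to 3 mg who took only 6 mg to Week 16 and 3 mg afterwards.

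1. The first exception fails, because the wrong treatment did not last the whole study.
2. The second fails, because the later doses match the assignment.
3. The participant therefore stays under 3 mg in the 16-week table without having taken 3 mg in those weeks. With 25 in the arm, this shifts a percentage by up to 1/25 = 4 points.

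The fault needs an active-arm assignment. A participant randomized to placebo who took only 6 mg to Week 16 and was then re-randomized to 6 mg meets the first exception; if re-randomized to 3 mg, the second applies. Either way the 16-week table shows 6 mg, the treatment taken.

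**The case for a change.** The best case for a change has four parts.

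- **Literal reading.** The sentence has no exception, and the wrong-treatment exceptions do not move crossovers, because their placebo doses matched their assignment. This is correct. However, 10.3.2 refers to the as-treated population generically, while 10.2 has two populations with that name, each tied to a period. The sentence can be read as covering both, in which case the SAP author overrules nothing.
- **Weeks 16-52 matter.** One-year safety is a stated aim, laboratory tests and ECGs continue in Table 2-3, and the safety objective in Table 4-1 has no Week 16 limit. All true: 2,700 of 3,500 planned participant-weeks on deucravacitinib (50 × 52 + 25 × 36 = 3,500), or 77%, fall after Week 16. But that objective is a comparison with placebo, which ends at Week 16. The length of the later period makes the choice of grouping worth stating; it does not show that a wrong choice was made.
- **Deferral to the SAP is not a cure.** A protocol sentence that can be misread is better tidied. That stands as an editorial remark. But participant selection is the very item section 10.3 assigns to the SAP, and the redacted contents entry after 10.3.2 means that silence in the readable text cannot be counted as an omission.
- **The whole-study wording is a true mismatch.** It is, and it would remain even if As Treated were meant only for the first 16 weeks. Yet it needs sixteen weeks of solely wrong treatment under central IRT assignment, followed by the correct dose. The definition's opening line already ties that population to the placebo-controlled part, so an analyst would apply the rule there.

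Reporting exposure-adjusted rates from the first active dose would be reasonable, but it is a reporting preference and not the repair of an error.

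**Conclusion.** The concern does not call for a change. The described 16-week safety comparison uses the right population and the right groups. For Weeks 16-52 the protocol supplies a suitable by-sequence population and leaves its assignment to be spelled out; given four named sequences, an analyst would hardly tabulate crossovers as placebo.

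The one-third figure is the planned crossover share of Week 16-52 exposure, assuming 25 per arm and equal retention (25.9% to 41.7% if retention differs between 70% and 100%). It would measure misattribution only if a table by initial arm were planned, and none is shown. The wrong-treatment wording is a clerical slip worth at most about 4 percentage points per affected participant, with no realistic prospect of arising.

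The conclusion rests on the readable text. It would be different if the SAP or the redacted material specified Week 16-52 safety tables by initial arm.

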10.3.4 Interim Analyses

[figure not shown]
Not applicable.

12 APPENDICES

APPENDIX 1 ABBREVIATIONS AND TRADEMARKS

Term	Definition
ACLE	acute cutaneous lupus erythematosus
ACR	American College of Rheumatology
ADME	absorption, distribution, metabolism, and excretion
AE	adverse event
[REDACTED]	[REDACTED]
ALT	alanine aminotransferase
anti-dsDNA	anti-double stranded deoxyribonucleic acid (antibody)
anti-HBs	anti-hepatitis B surface antibody
APS	antiphospholipid antibody syndrome
[REDACTED]	[REDACTED]
AST	aspartate aminotransferase
[REDACTED]	[REDACTED]
BID	twice a day
BMI	body mass index
BMS	Bristol-Myers Squibb (Company)
C3	complement 3
C4	complement 4
CCLE	chronic cutaneous lupus erythematosus
CI	confidence interval
[REDACTED]	[REDACTED]
CLASI	Cutaneous Lupus Erythematosus Disease Area and Severity Index
CLASI-50	50% improvement from baseline in CLASI-A score
CLASI-A	CLASI activity (score)
CLASI-D	CLASI damage (score)
CLE	cutaneous lupus erythematosus
[REDACTED]	[REDACTED]
CONSORT	Consolidated Standards of Reporting Trials
COVID-19	coronavirus disease of 2019

Term	Definition
CR	complete response
CS	corticosteroid(s)
DLE	discoid lupus erythematosus
DMC	Data Monitoring Committee
ECG	Electrocardiogram
EOT	End of Treatment
ET	Early Termination
FDA	Food and Drug Administration
FSH	follicle-stimulating hormone
FU	Follow-up (Period)
HBsAg	hepatitis B surface antigen
HIV	human immunodeficiency virus
IB	Investigator's Brochure
IBD	inflammatory bowel disease
ICF	Informed Consent Form
IEC	Independent Ethics Committee

Term	Definition
IFN(α , β , γ)	interferon (alpha, beta, gamma)
[REDACTED]	[REDACTED]
IGRA	interferon-gamma release assay
IL	Interleukin
IMP	Investigational Medicinal Product
IP	Investigational Product
IRB	Institutional Review Board
[REDACTED]	[REDACTED]
IRT	Interactive Response Technology
[REDACTED]	[REDACTED]
IU	international unit
IV	Intravenous
JAK	Janus kinase
[REDACTED]	[REDACTED]
LE	Lupus Erythematosus
LET	lupus erythematosus tumidus
[REDACTED]	[REDACTED]
LSMEANS	least-squares mean
[REDACTED]	[REDACTED]
MD	Doctor of Medicine
[REDACTED]	[REDACTED]
[REDACTED]	[REDACTED]
MOA(s)	mechanism(s) of action
[REDACTED]	[REDACTED]
[REDACTED]	[REDACTED]
NSAID	nonsteroidal anti-inflammatory drug
NYHA	New York Heart Association
OCS	oral corticosteroid(s)
PA	Posterioranterior

Term	Definition
UPCR	urine protein/creatinine ratio
US	United States
UV	Ultraviolet
[REDACTED]	[REDACTED]
[REDACTED]	[REDACTED]
WOCBP	women of childbearing potential

APPENDIX 2 STUDY GOVERNANCE CONSIDERATIONS

The term 'Participant' is used in the protocol to refer to a person who has consented to participate in the clinical research study. The term 'Subject' used in the CRF is intended to refer to a person (Participant) who has consented to participate in the clinical research study.

REGULATORY AND ETHICAL CONSIDERATIONS

GOOD CLINICAL PRACTICE

This study will be conducted in accordance with:

- Consensus ethical principles derived from international guidelines including the Declaration of Helsinki and Council for International Organizations of Medical Sciences (CIOMS) International Ethical Guidelines
- Applicable International Council for Harmonisation (ICH) Good Clinical Practice (GCP) Guidelines
- Applicable laws, regulations, and requirements

The study will be conducted in compliance with the protocol. The protocol and any amendments and the participant informed consent will receive approval/favorable opinion by Institutional Review Board/Independent Ethics Committee (IRB/IEC), and regulatory authorities according to applicable local regulations prior to initiation of the study.

All potential serious breaches must be reported to the Sponsor or designee immediately. A potential serious breach is defined as a Quality Issue (eg, protocol deviation, etc) that is likely to affect, to a significant degree one or more of the following: (1) the physical, safety or mental integrity of one or more subjects/participants; (2) the scientific value of the trial (eg, reliability and robustness of generated data). Items (1) or (2) can be associated with either GCP Regulation(s) or Trial protocol(s).

Personnel involved in conducting this study will be qualified by education, training, and experience to perform their respective tasks.

This study will not use the services of study personnel where sanctions have been invoked or where there has been scientific misconduct or fraud (eg, loss of medical licensure, debarment).

INSTITUTIONAL REVIEW BOARD/INDEPENDENT ETHICS COMMITTEE

Before study initiation, the investigator must have written and dated approval/favorable opinion from the IRB/IEC for the protocol, consent form, participant recruitment materials (eg, advertisements), and any other written information to be provided to subjects/participants.

The investigator, Sponsor or designee should provide the IRB/IEC with reports, updates and other information (eg, expedited safety reports, amendments, and administrative letters) according to regulatory requirements or institution procedures.

The investigator is responsible for providing oversight of the conduct of the study at the site and adherence to requirements of the following where applicable:

- ICH guidelines,
- United States Code of Federal Regulations, Title 21, Part 50 (21CFR50)
- European Union Directive 2001/20/EC; or
- European Regulation 536/2014 for clinical studies (if applicable),
- European Medical Device Regulation 2017/745 for clinical device research (if applicable),
- the IRB/IEC
- and all other applicable local regulations.

COMPLIANCE WITH THE PROTOCOL AND PROTOCOL REVISIONS

The investigator should not implement any deviation or change to the protocol without prior review and documented approval/favorable opinion of an amendment from the IRB/IEC (and if applicable, also by local health authority) except where necessary to eliminate an immediate hazard(s) to study subjects/participants.

If a deviation or change to a protocol is implemented to eliminate an immediate hazard(s) prior to obtaining relevant approval/favorable opinion(s) the deviation or change will be submitted, as soon as possible to:

- IRB/IEC
- Regulatory Authority(ies), if applicable by local regulations (per national requirements)

Documentation of approval/favorable opinion signed by the chairperson or designee of the IRB(s)/IEC(s) and if applicable, also by local health authority must be sent to BMS.

If an amendment substantially alters the study design or increases the potential risk to the participant: (1) the consent form must be revised and submitted to the IRB(s)/IEC(s) for review and approval/favorable opinion; (2) the revised form must be used to obtain consent from subjects/participants currently enrolled in the study if they are affected by the amendment; and (3) the new form must be used to obtain consent from new subjects/participants prior to enrollment.

If the revision is done via an administrative letter, investigators must inform their IRB(s)/IEC(s).

FINANCIAL DISCLOSURE

Investigators and sub-Investigators will provide the Sponsor with sufficient, accurate financial information in accordance with local regulations to allow the Sponsor to submit complete and accurate financial certification or disclosure statements to the appropriate health authorities. Investigators are responsible for providing information on financial interests during the course of the study and for 1 year after completion of the study.

INFORMED CONSENT PROCESS

Investigators must ensure that subjects/participants are clearly and fully informed about the purpose, potential risks, and other critical issues regarding clinical studies in which they volunteer to participate.

In situations where consent cannot be given by subjects/participants, their legally acceptable representatives (as per country guidelines) are clearly and fully informed about the purpose, potential risks, and other critical issues regarding clinical studies in which the participant volunteers to participate.

Sponsor or designee will provide the investigator with an appropriate (ie, Global or Local) sample informed consent form which will include all elements required by ICH, GCP and applicable regulatory requirements. The sample informed consent form will adhere to the ethical principles that have their origin in the Declaration of Helsinki.

The investigator or his/her representative must:

Obtain the IRB/IEC's written approval/favorable opinion of the written informed consent form and any other information to be provided to the subjects/participants, prior to the beginning of the study, and after any revisions are completed for new information.

- Provide a copy of the consent form and written information about the study in the language in which the participant is most proficient prior to clinical study participation. The language must be non-technical and easily understood.
- Explain the nature of the study to the participant and answer all questions regarding the study.
- Inform participant that his/her participation is voluntary. Participant or his/her legally acceptable representative will be required to sign a statement of informed consent that meets the requirements of 21 CFR 50, local regulations, ICH guidelines, Health Insurance Portability and Accountability Act (HIPAA) requirements, where applicable, and the IRB/IEC or study center.
- Allow time necessary for participant or participant's legally acceptable representative to inquire about the details of the study.
- Obtain an informed consent signed and personally dated by the participant or the participant's legally acceptable representative and by the person who conducted the informed consent discussion.
- Include a statement in participant's medical record that written informed consent was obtained before participant was enrolled in the study and the date the written consent was obtained. The authorized person obtaining the informed consent must also sign the ICF.
- Re-consent participant to the most current version of the ICF(s) during his/her participation in the study, as applicable.

If informed consent is initially given by a participant's legally acceptable representative or legal guardian, and the participant subsequently becomes capable of making and communicating his or her informed consent during the study, consent must additionally be obtained from the participant.

Revise the informed consent whenever important new information becomes available that is relevant to the participant's consent. The investigator, or a person designated by the investigator, should fully inform the participant or the participant's legally acceptable representative or legal guardian, of all pertinent aspects of the study and of any new information relevant to the participant's willingness to continue participation in the study. This communication should be documented.

The confidentiality of records that could identify subjects/participants must be protected, respecting the privacy and confidentiality rules applicable to regulatory requirements, the subjects'/participants' signed ICF and, in the US, the subjects'/participants' signed HIPAA Authorization.

The consent form must also include a statement that BMS and regulatory authorities have direct access to participant records.

Subjects/participants unable to give their written consent (eg, stroke or subjects/participants with or severe dementia) may only be enrolled in the study with the consent of a legally acceptable representative. The participant must also be informed about the nature of the study to the extent compatible with his or her understanding, and should this participant become capable, he or she should personally sign and date the consent form as soon as possible. The explicit wish of a participant who is unable to give his or her written consent, but who is capable of forming an opinion and assessing information to refuse participation in, or to be withdrawn from, the clinical study at any time should be considered by the investigator.

The rights, safety, and well-being of the study subjects/participants are the most important considerations and should prevail over interests of science and society.

BMS COMMITMENT TO DIVERSITY IN CLINICAL TRIALS

The mission of BMS is to transform patients' lives through science by discovering, developing, and delivering innovative medicines that help them prevail over serious diseases.

BMS is committed to doing its part to ensure that patients have a fair and just opportunity to achieve optimal health outcomes.

BMS is working to improve the recruitment of a diverse participant population with the goal that the clinical trial becomes more reflective of the real-world population and the people impacted by the diseases studied.

DATA PROTECTION, DATA PRIVACY, AND DATA SECURITY

BMS collects and processes personal data of study participants, patients, health care providers, and researchers for biopharmaceutical research and development to advance innovative, high-quality medicines that address the medical needs of patients. BMS ensures the privacy, protection, and confidentiality of such personal data to comply with applicable laws. To achieve these goals, BMS has internal policies that indicate measures and controls for processing personal data. BMS adheres to these standards to ensure that collection and processing of personal data are limited and proportionate to the purpose for which BMS collects such personal data. This purpose is clearly and unambiguously notified to the individual at the time of collection of personal data. In the true spirit of science, BMS is dedicated to sharing clinical trial information and data with participants, medical/research communities, the media, policy makers, and the general public. This is done in a manner that safeguards participant privacy and informed consent while respecting the integrity of national regulatory systems. Clinical trial data, health-related research, and pharmacovigilance activities on key-coded health data transferred by BMS across national borders is done in compliance with the relevant data protection laws in the country and GCP requirements.

BMS protects Personal Information with adequate and appropriate security controls as indicated under the data protection laws. To align with the recommended security standards, BMS has adopted internal security standards and policies to protect personal data at every stage of its processing.

To supplement these standards, BMS enters into Clinical Trial Agreements (CTAgs) with confidentiality obligations to ensure proper handling and protection of personal data by third parties accessing and handling personal data.

BMS takes unauthorized access and disclosure of Personal Information very seriously. BMS has adopted the security standards that include National Institute of Standards and Technology Cybersecurity Framework for studies in the US. BMS aligns with these standards to continuously assess and improve its ability to protect, detect, and respond to cyber attacks and other unauthorized attempts to access personal data. These standards also aid in mitigating possible adverse effects. Furthermore, BMS Information Technology has defined 6 principles to protect our digital resources and information:

- 1) Responsibilities of IT Personnel
- 2) Securing the BMS Digital Infrastructure
- 3) Identity and Access Management
- 4) External Partner Connections
- 5) Cyber Threat Detection and Response
- 6) Internal Cyber Incident Investigation

SOURCE DOCUMENTS

Source documents provide evidence for the existence of the participant and substantiate the integrity of the data collected. Source documents are filed at the investigator's site.

Data reported on the CRF or entered in the electronic CRF (eCRF) that are transcribed from source documents must be consistent with the source documents or the discrepancies must be explained.

- The investigator may need to request previous medical records or transfer records, depending on the study. Also, current medical records must be available.
- Definitions of what constitutes source data can be found in the Site Process and Source Documentation (SPSD) form.

The Investigator is responsible for ensuring that the source data are accurate, legible, contemporaneous, original and attributable, whether the data are hand-written on paper or entered electronically. If source data are created (first entered), modified, maintained, archived, retrieved, or transmitted electronically via computerized systems (and/or any other kind of electronic devices) as part of regulated clinical trial activities, such systems must be compliant with all applicable laws and regulations governing use of electronic records and/or electronic signatures. Such systems may include, but are not limited to, electronic medical/health records (EMRs/EHRs),

adverse event tracking/reporting, protocol required assessments, and/or drug accountability records).

When paper records from such systems are used in place of electronic format to perform regulated activities, such paper records should be certified copies. A certified copy consists of a copy of original information that has been verified, as indicated by a dated signature, as an exact copy having all of the same attributes and information as the original.

STUDY TREATMENT RECORDS

Records for study treatments (whether supplied by BMS, its vendors, or the site) must substantiate study treatment integrity and traceability from receipt, preparation, administration, and through destruction or return. Records must be made available for review at the request of BMS/designee or a Health Authority.

If	Then
Supplied by BMS (or its vendors):	
Records or logs must comply with applicable regulations and guidelines and should include:
 
• amount received and placed in storage area• amount currently in storage area• label identification number or batch number• amount dispensed to and returned by each participant, including unique participant identifiers• amount transferred to another area/site for dispensing or storage• nonstudy disposition (eg, lost, wasted)• amount destroyed at study site, if applicable• amount returned to BMS• retain samples for bioavailability/bioequivalence/biocomparability, if applicable• dates and initials of person responsible for Investigational Product dispensing/accountability, as per the Delegation of Authority Form.
Sourced by site, and not supplied by BMS or its vendors (examples include IP sourced from the sites stock or commercial supply, or a specialty pharmacy)	The investigator or designee accepts responsibility for documenting traceability and study treatment integrity in accordance with requirements applicable under law and the SOPs/standards of the sourcing pharmacy.

BMS or designee will provide forms to facilitate inventory control if the investigational site does not have an established system that meets these requirements.

CASE REPORT FORMS

An investigator is required to prepare and maintain adequate and accurate case histories designed to record all observations and other data pertinent to the investigation on each individual treated or entered as a control in the investigation. Data that are derived from source documents and reported on the CRF must be consistent with the source documents or the discrepancies must be explained. Additional clinical information may be collected and analyzed in an effort to enhance understanding of product safety. CRFs may be requested for AEs and/or laboratory abnormalities that are reported or identified during the course of the study.

For sites using the Sponsor or designee electronic data capture tool, electronic CRFs will be prepared for all data collection fields except for fields specific to SAEs and pregnancy, which will be reported on the electronic SAE form and Pregnancy Surveillance form, respectively. If electronic SAE form is not available, a paper SAE form can be used. Spaces may be left blank only in those circumstances permitted by study-specific CRF completion guidelines provided by Sponsor or designee.

The confidentiality of records that could identify subjects/participants must be protected, respecting the privacy and confidentiality rules in accordance with the applicable regulatory requirement(s).

The investigator will maintain a signature sheet to document signatures and initials of all persons authorized to make entries and/or corrections on CRFs.

The completed CRF, SAE/pregnancy CRFs, must be promptly reviewed, signed, and dated by the investigator or qualified physician who is a subinvestigator and who is delegated this task on the Delegation of Authority Form. Subinvestigators in Japan may not be delegated the CRF approval task. For electronic CRFs, review and approval/signature is completed electronically through the BMS electronic data capture tool. The investigator must retain a copy of the CRFs including records of the changes and corrections.

Each individual electronically signing electronic CRFs must meet Sponsor or designee training requirements and must only access the BMS electronic data capture tool using the unique user account provided by Sponsor or designee. User accounts are not to be shared or reassigned to other individuals

MONITORING

Monitoring details describing strategy, including definition of study critical data items and processes (eg, risk-based initiatives in operations and quality such as risk management and mitigation strategies and analytical risk-based monitoring), methods, responsibilities, and requirements, including handling of noncompliance issues and monitoring techniques (central, remote, or on-site monitoring) are provided in the monitoring plan

Representatives of BMS must be allowed to visit all study site locations periodically to assess the data quality and study integrity. On site they will review study records and directly compare them with source documents, discuss the conduct of the study with the investigator, and verify that the facilities remain acceptable.

In addition, the study may be evaluated by Sponsor or designee internal auditors and government inspectors who must be allowed access to CRFs, source documents, other study files, and study facilities. BMS audit reports will be kept confidential.

The investigator must notify BMS promptly of any inspections scheduled by regulatory authorities, and promptly forward copies of inspection reports to Sponsor or designee.

RECORDS RETENTION

The investigator (or head of the study site in Japan) must retain all study records and source documents for the maximum period required by applicable regulations and guidelines, or institution procedures, or for the period specified by BMS or designee, whichever is longer. The investigator (or head of the study site in Japan) must contact BMS prior to destroying any records associated with the study.

BMS or designee will notify the investigator (or head of the study site in Japan) when the study records are no longer needed.

If the investigator withdraws from the study (eg, relocation, retirement), the records shall be transferred to a mutually agreed upon designee (eg, another investigator, study site, IRB). Notice of such transfer will be given in writing to BMS or designee.

RETURN OF STUDY TREATMENT

For this study, study treatments (those supplied by BMS, a vendor or sourced by the investigator) such as partially used study treatment containers, vials and syringes may be destroyed on site.

If	Then
Study treatments supplied by BMS (including its vendors)	Any unused study treatments supplied by BMS can only be destroyed after being inspected and reconciled by the responsible Study Monitor unless study treatments containers must be immediately destroyed as required for safety, or to meet local regulations (eg, cytotoxics or biologics). If study treatments will be returned, the return will be arranged by the responsible Study Monitor.
Study treatments sourced by site, not supplied by BMS (or its vendors) (examples include study treatments sourced from the sites stock or commercial supply, or a specialty pharmacy)	It is the investigator's or designee's responsibility to dispose of all containers according to the institutional guidelines and procedures.

It is the investigator's or designee's responsibility to arrange for disposal, provided that procedures for proper disposal have been established according to applicable federal, state, local, and institutional guidelines and procedures, and provided that appropriate records of disposal are kept. The following minimal standards must be met:

- On-site disposal practices must not expose humans to risks from the drug.
- On-site disposal practices and procedures are in agreement with applicable laws and regulations, including any special requirements for controlled or hazardous substances.
